3. SAMPLE SIZE DETERMINATION

Assuming a treatment difference of 5 points in change from baseline in NPI-C A+A score between seltorexant 20 mg and placebo, a standard deviation of 10 (effect size of 0.5), and a 15% drop-out rate during the 6-week double-blind phase, 86 participants (randomized in 1:1 ratio to placebo and seltorexant 20 mg) will need to be enrolled in the double-blind phase, in order to achieve 80% power to detect treatment difference, at one-sided 0.1 significance level.

4. POPULATIONS (ANALYSIS SETS) FOR ANALYSIS

Analysis Sets	Description		
All Enrolled	All participants who sign the ICF		
All Randomized	All participants who were randomized in the study.		
Full	All randomized participants who take at least 1 dose of		
	study intervention		
Follow-up	All randomized participants who provide data in the		
	follow-up visit(s).		
Safety	All randomized participants who take at least 1 dose of		
	study intervention		

5. STATISTICAL ANALYSES

5.1. General Considerations

5.1.1. Visit Windows

As participants do not always adhere to the protocol visit schedule, the following rules are applied to assign actual visits to analysis visits. Listed below are the visit windows and the target days for each visit. The reference day is Study Day 1. If a participant has 2 or more actual visits in 1 visit window, the visit closest to the target day will be used as the protocol visit for that visit window. The other additional visit(s) will not be used in the summaries or

Statistical Analysis Plan 42847922ALZ2001

analyses, but they can be used for determination of clinically important endpoints. If 2 actual visits are equidistant from the target day within a visit window, the later visit is used.

All assignments will be made in chronological order. Once a visit date is assigned to a visit window, it will no longer be used for a later time point except for the endpoint. Listed below (Table 1) are the analysis visit windows and the target days for each visit defined in the protocol.

		Scheduled			Target
	Analysis	Visit	Time Interval	Time Interval	Time Point
Parameter	Phase	Number	(label on output)	(Day)*	(Day)*
NPI-12	SCR	1	Screening	<1	
SDI	DB	2	Baseline (DB)	<=1	1
C-SSRS		4	Day 15	2 to 22	15
_		5	Day 29	23 to 36	29
		6	Day 43	37 to End of DB	43
		DB final visit	Endpoint (DB)	2 to End of DB	
	FU (DB)	7	Day 57	End of DB + 1 to End of FU	10
			Day 15 EW	2 to 22	15
			Day 29 EW	23 to 36	29
			Day 43 EW	37 to 48	43
			Day 57 EW	49 to End of FU	57
NPI-C	DB	2	Baseline (DB)	<=1	1
		4	Day 15	2 to 22	15
		5	Day 29	23 to 36	29
		6	Day 43	37 to End of DB	43
		DB final	Endpoint (DB)	2 to End of DB	
	FU (DB)	7	Day 57	End of DB + 1	10
			-	to End of FU	
			Day 15 EW	2 to 22	15
			Day 29 EW	23 to 36	29
			Day 43 EW	37 to 48	43
			Day 57 EW	49 to End of FU	57
CMAI-C	DB	2	Baseline (DB)	<=1	1
ADAS-Cog-14		4	Day 15	2 to 29	15
		6	Day 43	30 to End of DB	43
		DB final	Endpoint (DB)	2 to End of DB	
GDSI	DB	2	Baseline (DB)	<=1	1
		6	Day 43	2 to End of DB	43
		DB final visit	Endpoint (DB)	2 to End of DB	
MMSE	SCR	1	Screening	<1	
	DB	2	Baseline (DB)	<=1	
		6	Day 43	2 to End of DB	43
		DB final visit	Endpoint (DB)	2 to End of DB	
Weight	SCR	1	Screening	<1	
Labs	DB	2	Baseline (DB)	<=1	1
		DB final visit	Endpoint (DB)	2 to End of DB	
Vital Signs	SCR	1	Screening	<1	
[DB	2	Baseline (DB)	<=1	1
		4	Day 15	2 to 29	15
		6	Day 43	30 to End of DB	43

Table 1- Visit Windows

CONFIDENTIAL – FOIA Exemptions Apply in U.S.

 Statistical Analysis Plan 42847922ALZ2001

 DB final visit
 Endpoint (DB)
 2 to End of DB

		Scheduled			Target Time
	Analysis Phase	Visit Number	Time Interval (label	Time Interval	Point (Day)*
Parameter			on output)	(Day)*	
	FU (DB)	7	Day 57	End of $DB + 1$	10
				to End of FU	
			Day 15 EW	2 to 29	15
			Day 43 EW	30 to 48	43
			Day 57 EW	49 to End of FU	57
12-lead ECG	SCR	1	Screening	<1	
	DB	2	Baseline (DB)	<=1	1
		6	Day 43	2 to End of DB	43
		DB final visit	Endpoint (DB)	2 to End of DB	
PWC-20	DB	DB final visit	Endpoint (DB)	2 to End of DB	43
	FU (DB)	7	Day 57	End of DB + 1	10
			-	to End of FU	
Actigraphy	SCR		Screening	<1	
	DB		Baseline (DB)	-7 to -1	
			Week 1	1 to 7	
			Week 2	8 to 14	
			Week 3	15 to 21	
			Week 4	22 to 28	
			Week 5	29 to 35	
			Week 6	36 to End of DB	

* Relative to the first day of the respective phases for DB and FU (DB) phase; Assignment of visits to the FU (DB) will be made to the assessments that were recorded after double-blind treatment stop date. Participants who discontinue DB prior to Day 35 will have additional follow-up visits performed every 2 weeks until Day 50-57 - the follow-up data from these participants are assigned relative to the first day of DB phase with visit labels ending with EW.

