Visit 2 will occur on Day 1 (baseline). Study restrictions and any changes in inclusion/exclusion criteria will be reviewed, and an alcohol breath test and urine drug screen performed. Other assessments will be completed as per the SoA at this and subsequent visits.

Upon completion of Visit 2 assessments, eligible participants will be randomized and receive the study medication to take home for the double-blind treatment period, including instructions and a medication diary. Participants and study partners will be reminded about the use of the actigraphy device.

Visit 3

Approximately 7 days after Visit 2 (baseline), the participant and their study partner will be contacted remotely (ie, by telephone or videoconference) and queried for AEs that may have occurred between the last visit and remote follow up, and overall study drug dosing compliance and tolerance, and medication diary completion.

Visit 4

Visit 4 will take place at the end of Week 2 of the double-blind treatment period.

Upon completion of Visit 4 assessments, participants and study partners will be reminded about the use of the actigraphy device.

Visit 5

Visit 5 will be at the end of Week 4 of the double-blind period and is preferred to be done on-site; if done remotely, the NPI-C should be conducted by videoconference if possible (with audio-recording)

Visit 6

Visit 6 will be at the end of Week 6 of the double-blind treatment period or at the time of early withdrawal from study treatment. At Visit 6, participants and study partners will return the actigraphy device.

All participants who discontinue study drug in the DB treatment phase, will have an Early Withdrawal visit (Visit 6 in the Schedule of Activities [SoA]), preferably the day after the last dose. After completion of this visit, the participant enters the follow-up phase. All participants who

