5.1.2. Analysis Phases

Double-Blind Analysis Phase

The analysis reference start date of the double-blind analysis phase is the date of the first dose of double-blind study intervention. The analysis reference end date of the double-blind analysis phase is the maximum of the date of the last visit in the double-blind phase and date of completion or early withdrawal from the double-blind phase. For randomized participants who did not receive any study intervention in the double-blind phase, both analysis reference start and end dates are missing for the double-blind analysis phase.

Assignment of adverse events to double-blind analysis phase is described separately in Section 5.6.2.

Follow-up Phase

Start and end dates for the follow-up phase are only defined for participants who continued into the follow-up phase. The analysis reference start date of the follow-up analysis phase is the day after the reference end date for the double-blind analysis phase. The analysis reference end date of the follow-up analysis phase is the maximum of the last follow-up visit date or the study disposition date.

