5.3.1. Definition

The primary efficacy endpoint is the change in NPI-C A+A score from baseline (DB) to Day 43.

The Neuropsychiatric Inventory-Clinician Rating (NPI-C) (de Medeiros 2010) is an instrument that

Statistical Analysis Plan 42847922ALZ2001

expands upon the items and 12 symptom domains of the original NPI. The modified rating methodology of the NPI-C incorporates the expert clinician's impressions to the data provided by the patients and caregivers. For each domain, the domain score will be calculated as the sum of clinician severity ratings (from 0=does not occur to 3=severe) for each item. NPI-C A+A score is the sum of the domain scores from the Agitation and Aggression domains at a given time point, and ranges from 0 to 63. Higher scores represent a more serious condition.

Negative changes in NPI-C A+A represent improvement.

Two estimands are defined for the primary endpoint: The primary estimand is Estimand 1, and the supplementary estimand is Estimand 2.

The sections below describe the primary analyses performed for each primary and supplementary estimand. For treatment policy strategy, data collected after participants experienced intercurrent events will be included in analyses; for hypothetical strategy, data collected after participants experienced an intercurrent event of treatment switch will not be included in analyses. Otherwise, data observed up to and including DB disposition day will be included.

5.3.2. Estimand 1

Estimand 1 will be the **primary estimand**. The analysis will be performed on the full analysis set.

Primary Trial Objective: To evaluate the efficacy of seltorexant 20 mg compared with placebo in improving agitation/aggression symptoms in participants with probable AD with clinically significant agitation/aggression.

Estimand Scientific Question of Interest: What is the benefit in improving agitation/aggression symptoms from seltorexant 20 mg versus placebo in adults and elderly participants with probable AD with clinically significant agitation/aggression based on the change from baseline in NPI-C A+A score if the participants take study intervention as directed?

Estimand 1 is defined by the following 5 components:

Study Intervention:

- Experimental: Seltorexant dose of 20 mg
- Control: Placebo

Population: Participants with probable AD with clinically signification agitation/aggression, as reflected by the inclusion/exclusion criteria.

Variable: Change in NPI-C A+A total score from baseline to Day 43

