Summary Measure: Difference in intervention means

Intercurrent Events	Name of Strategy for Addressing Intercurrent Events and Its Description
1. Treatment discontinuation of study drug without switching	Hypothetical strategy: as if the intercurrent event had not occurred
2. Switch of treatment	Hypothetical strategy: see above
3. Allowed rescue medication	Treatment policy strategy: all observed values of
(including use after treatment	the endpoint are used regardless of whether or not
discontinuation, but prior to DB	the participant had experienced this intercurrent
disposition)	event

Intercurrent events and their corresponding strategies:

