5.3.2.1. Analysis Methods

5.3.2.1.1. Primary Analysis

Descriptive statistics of the actual values and the change from baseline (DB) to each postbaseline time point will be presented for NPI-C A+A score by intervention group.

NPI-C A+A score will be analyzed by a Mixed-Effect Model for Repeated Measures (MMRM) based on observed case. The fixed terms included in the model will be intervention group, baseline NPI Sleep domain score category (per eDC), time, and time-by-intervention interaction, and baseline (DB) NPI-C A+A total score as a covariate. The within-subject covariance between visits will be estimated via an unstructured variance-covariance matrix. In case of convergence problems, alternative variancecovariance structures will be tried in the following order, with the first structure that converges being used in the analysis: heterogeneous Toeplitz, standard Toeplitz, and AR(1) with separate subject random effect; in addition, a robust sandwich variance estimator will be used to address the potential impact of covariance matrix misspecification on the estimation and testing of treatment effect. The Kenward-Roger method will be used for approximating the denominator degrees of freedom. Comparison between seltorexant and placebo at Day 43 will be performed using the appropriate contrast. Difference in least square means and 2-sided 80% CI will be presented.

Least squares mean changes from baseline(DB) (+/- SE) will be presented graphically over time.

No multiplicity adjustment will be included for efficacy endpoints.

5.3.3. Estimand 2

Estimand 2 will be a **supplementary estimand**. The analysis will be performed on the full analysis set.

All components as described under Estimand 1 (Section 5.3.2) apply to Estimand 2 except for the strategy for addressing intercurrent events.

Intercurrent events and their corresponding strategies:

	Statistical Analysis Plan 42847922ALZ2001
	Name of Strategy for Addressing Intercurrent
Intercurrent Events	Events and Its Description
1. Treatment discontinuation of study drug	Treatment policy strategy: all observed values of
without switching	the endpoint are used regardless of whether or not
	the participant had experienced this intercurrent
	event
2. Switch of treatment	Hypothetical strategy: as if the intercurrent event
	had not occurred
3. Allowed rescue medication	Treatment policy strategy: all observed values
(including use after treatment	of the endpoint are used regardless of whether

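### Do the SAP's three wordings for the end of double-blind data leave it unclear which NPI-C scores enter the primary analysis?

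*SAP*

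**What the plan says.** Three places in the SAP bear on where double-blind data stop.

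- **Section 5.1.1, Table 1 footnote.** "Assignment of visits to the FU (DB) will be made to the assessments that were recorded after double-blind treatment stop date". The footnote's stop date is not defined and the term is not used elsewhere.
- **Section 5.1.2.** The double-blind analysis phase ends at "the maximum of the date of the last visit in the double-blind phase and date of completion or early withdrawal from the double-blind phase", and follow-up begins the next day. The follow-up phase ends at "the maximum of the last follow-up visit date or the study disposition date", so a disposition date and a visit date are treated as things that can differ.
- **Section 5.3.1.** After the treatment-switch rule, the data rule for the estimands reads: "Otherwise, data observed up to and including DB disposition day will be included". Disposition day is not defined. The Estimand 1 table in Section 5.3.2 uses the term again for rescue medication taken after treatment "discontinuation, but prior to DB" disposition.

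Other text fixes the context. In Table 1, Visit 6 is a double-blind row for NPI-C, with a window from Day 37 to the end of the double-blind phase; the follow-up row starts one day after that. Protocol Section 4.1 says of the early-withdrawal visit: "After completion of this visit, the participant enters the follow-up phase". Protocol Section 4.4 makes completion of the double-blind phase depend on completing the Day 43 visit. The Schedule of Activities ends dosing on the night of Day 42, while both documents give the treatment phase as 43 days.

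**The concern.** Which scores count as double-blind data determines the input to the primary model, an MMRM run "based on observed case". Two undefined dates beside a defined one could let two programmers build different datasets.

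If the footnote's stop date meant the last dose (Day 42), an on-schedule Visit 6 on Day 43 would be filed under follow-up and the Day 43 contrast would lose its data. If DB disposition day meant an administrative withdrawal date, an early-withdrawal NPI-C taken after it would be a double-blind visit under Section 5.1.2 but past the cut-off in Section 5.3.1. A participant who stops before Visit 4 has no other post-baseline NPI-C, so that person would drop out of the model. Such participants may well have left because of worsening symptoms or an adverse event, which is why the rule deserves a check.

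**Working it through.** **Step 1: the plan's own figure.** Inputs from SAP Section 3: difference 5, SD 10, one-sided alpha 0.1, power 80%, dropout 15%.

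n per arm = 2 x [10 x (1.2816 + 0.8416) / 5]^2 = 36.06. The total is 72.13, rounded up to 73, and 73 / 0.85 = 85.9, giving 86. The stated sample size is reproduced and does not depend on the date rules.

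**Step 2: apply the date rules to example participants.** The days are illustrative. The third column uses Section 5.1.2. The last column takes disposition day to be the recorded completion or withdrawal date.

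| Participant | Last dose / recorded date / Visit 6 | 5.1.2 end date, phase of Visit 6 | Inside the 5.3.1 cut-off? |
|---|---|---|---|
| A. Completer on schedule | 42 / 43 / 43 | max(43, 43) = 43, double-blind | Yes, 43 <= 43 |
| B. Early withdrawal, recorded at the visit | 20 / 21 / 21 | max(21, 21) = 21, double-blind | Yes, 21 <= 21 |
| C. Early withdrawal, visit delayed | 20 / 21 / 24 | max(24, 21) = 24, double-blind | No, 24 > 21 |
| D. Withdrawal dated on the last-dose day | 20 / 20 / 21 | max(21, 20) = 21, double-blind | No, 21 > 20 |

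**Step 3: the footnote.** If its stop date is read as the last dose, Visit 6 goes to follow-up in all four rows, including A (43 > 42). That contradicts Table 1's own Visit 6 row, Section 5.1.2 and Protocol Section 4.1. A treatment phase of 43 days with dosing to Day 42 also shows that the phase outlasts the last dose. The only reading consistent with the rest is the end of the double-blind phase. On that reading the footnote changes no assignment.

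**Step 4: the disposition cut-off.** Row A cannot go wrong, because Protocol Section 4.4 ties completion to the Day 43 visit. Row D sits badly with the Estimand 1 rescue-medication row, which supposes an interval between stopping treatment and DB disposition; in D that interval is 20 - 20 = 0 days. The natural reading puts disposition at the early-withdrawal visit, as in B, where the two rules agree. Only row C is left unsettled by the text.

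**Step 5: how much row C could matter.** Early withdrawals at the planned rate: 86 x 0.15 = 12.9. The share whose Visit 6 falls after the recorded date is not given, so the number affected lies between 0 and 12.9. It is lower still because participants who die, are lost to follow-up or withdraw consent for assessments will generally have no Visit 6. Including the visit need not add a usable score either: "If a participant has 2 or more actual visits in 1 visit window, the visit closest to the target day will be used", so a scheduled visit may displace it.

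Suppose no early withdrawal contributes a Day 43 score. Then n = 86 x 0.85 = 73.1, the SE of the difference = 10 x sqrt(4 / 73.1) = 2.34, and power = Phi(5 / 2.339 - 1.2816) = Phi(0.856) = 0.804 (0.801 with the t distribution). That is the design target.

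**The case for a change.** The best case for acting is that Section 5.3.1 decides which post-discontinuation scores enter the primary analysis. Version 2.0 of the SAP revised that section to clarify data use, yet left the governing date undefined. The later-of-two-dates rule in Section 5.1.2 makes sense only if the last visit and the withdrawal date can differ. The protocol says the early-withdrawal visit should preferably be the day after the last dose but sets no upper limit on delay. Estimand 2 uses Day 43 in its rescue row, so the disposition term does work specific to Estimand 1. Aligning the terms would take a sentence and two replacements.

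Part of this stands. The two terms are undefined, and for a delayed early-withdrawal visit (row C) the text alone does not choose between Sections 5.1.2 and 5.3.1. It does not follow that a stated rule gives a wrong answer. Nothing in the documents shows that withdrawal will be recorded ahead of Visit 6. Nor is it clear that row C's score ought to be included: Estimand 1 handles discontinuation by a hypothetical strategy, and leaving out a score taken days after the last dose is defensible under it. A proposal to align the terms would itself have to allow that an earlier cut-off may be intended.

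**Conclusion.** The concern does not call for a change. The footnote affects no participant on the only reading that fits Table 1, Section 5.1.2 and the protocol. The Section 5.3.1 cut-off leaves completers untouched and agrees with Section 5.1.2 whenever early withdrawal is recorded at Visit 6, which is where the protocol and the rescue-medication row place it.

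The residue is a delayed early-withdrawal visit: somewhere from 0 to 12.9 participants at the assumed dropout, with no basis in the documents for a figure inside that range. Losing every Day 43 score from that group would leave the 73.1 participants and power of about 0.80 that the plan was built on. That bound assumes the planned 15% dropout and SD of 10, and it counts Day 43 scores only, ignoring what the MMRM borrows from earlier visits. It addresses precision, not possible bias from selective loss, which cannot be sized from the documents.

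This is a gap in terminology that analysts can fill by taking the Section 5.1.2 end date as the common reference.

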discontinue study drug in the DB treatment phase after Day 35 will have an Early Withdrawal visit (Visit 6 in the SoA) and a Follow-up visit (Visit 7 in the SoA). Participants who discontinue study drug prior to Day 35 are encouraged to continue with additional Follow-up visits every 2 weeks per the SoA until Day 57 (up to four Early Withdrawal Follow-up visits will be possible). At least one Early Withdrawal Follow-up visit needs to be conducted 2 weeks apart from the Early Withdrawal visit (EW Follow-up 1, which will include the assessments of Visit 7 in the SoA). These additional Follow-up visits may be done remotely (eg, tele- or videoconference; optional) or at the research site. If done remotely, the NPI-C should be conducted by videoconference, if possible.

Efficacy and safety assessments, sparse PK sampling, biomarkers sampling, and other study procedures will be performed at each visit per the SoA. If a participant withdraws from the study drug, the End of DB Treatment/Early Withdrawal visit assessments (including NPI-C/12) will be performed per the SoA, preferably on the day after the last dose or as soon as the participant and study partner are available for the assessment.

Entry to the follow-up phase should not be conducted in participants or study partners who withdraw consent for further study assessments; however, they should complete the End of DB treatment/EW visit if they are willing to do so.

Follow-Up Period-

Post-treatment Follow-up period (14 days after completion of the double-blind treatment period)

Visit 7 (Follow-up Visit) which may be done remotely or in person.

Participants who received at least 1 dose of study drug, except those who withdrew consent for the study or who are lost to follow-up, will complete follow-up assessments per the SoA approximately 14 days after the last dose of study drug.

For participants who have completed the DB treatment phase (at the End of DB Treatment phase), this follow-up visit is the last visit. All participants who discontinue study drug in the DB treatment phase, will have an End of DB treatment/EW visit (Visit 6 in the SoA) and a Follow-up visit (Visit 7 in the SoA). Participants who discontinue study drug prior to Day 35 are encouraged to continue after the Follow-up visit (Visit 7 in the SoA) with additional Follow-up visits, every 2 weeks per the SoA until Day 57.

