1.2. Study Design

This is a multicenter, DB randomized, parallel-group, placebo-controlled, 6-week study to assess the efficacy and safety of seltorexant 20mg in participants aged 55 to 85 years, inclusive, with probable AD with clinically significant agitation/aggression.

This study will consist of 3 phases: a screening phase (up to 28 days), a double-blind treatment phase (43 days), and a post-treatment follow-up phase (14 days after DB treatment phase).

Approximately 86 participants with probable AD and clinically significant agitation/aggression will be randomly assigned to receive placebo or seltorexant 20 mg in a 1:1 ratio for 6 weeks in the DB treatment phase. Randomization will be stratified by baseline NPI-12 sleep domain score (<4, ≥4) and community dwelling/assisted living.

Participants who discontinue early from study intervention in the DB treatment phase will be further assessed during additional follow-up visits every 2 weeks until Day 57.

Statistical Analysis Plan 42847922ALZ2001

Participants will take their assigned study intervention at home, once daily at bedtime during DB treatment phase.

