Descriptive statistics of the actual values and the change from baseline(DB) to each postbaseline time point will be presented for NPI-C A+A total score by intervention group. Under the treatment policy strategy, data from participants who discontinued the study drug only (intercurrent event 1 under this estimand) and provided additional follow-up data every 2 weeks until Day 43 will be included in this analysis.

Least squares mean changes from baseline(DB) (+/- SE) will be presented graphically over time.

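### SAP Table 1 ends the Day 43 EW window at Day 48 where the table's own pattern gives Day 50, which can cost a few early discontinuers an observed Day 43 score in Estimand 2; the Visit 7 target of day 10 also conflicts with the 14-day follow-up

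*SAP*

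**What the plan says.** SAP 5.1.1, Table 1, gives the same EW rows for NPI-12/SDI/C-SSRS and for NPI-C: Day 15 EW is 2 to 22, Day 29 EW is 23 to 36, Day 43 EW is 37 to 48, and Day 57 EW runs from 49 to the end of follow-up. Vital signs use 2 to 29, 30 to 48 and 49 onward. The targets are Days 15, 29, 43 and 57.

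The footnote states who receives these visits: "Participants who discontinue DB prior to Day 35 will have additional follow-up visits performed every 2 weeks until Day 50-57". It also states how they are counted: "the follow-up data from these participants are assigned relative to the first day of DB phase with visit labels ending with EW". Where visits compete, "If a participant has 2 or more actual visits in 1 visit window, the visit closest to the target day will be used", and the later one is taken if two are equally distant.

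SAP 5.3.3.1.1 brings these data into Estimand 2: off-drug participants who "provided additional follow-up data every 2 weeks until Day 43 will be included in this analysis". Values that are missing or unused are imputed. The copy-reference assumption applies in the seltorexant arm and missing at random in the placebo arm.

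For the ordinary follow-up visit (Visit 7, labelled Day 57), the FU (DB) rows give one open window and target day 10. Days in those rows are counted "Relative to the first day of the respective phases for DB and FU (DB) phase". SAP 5.1.2 adds: "The analysis reference start date of the follow-up analysis phase is the day after the reference end date for the double-blind analysis phase". SAP 1.2 describes "a post-treatment follow-up phase (14 days after DB treatment phase"), and Protocol 4.1 says the same: "Post-treatment Follow-up period (14 days after completion of the double-blind treatment period").

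**The concern.** The upper bound of 48 is the only boundary between two post-baseline targets that breaks the table's pattern. A visit on Day 49 is 6 days from Day 43 and 8 days from Day 57, yet it is labelled Day 57 EW. Day 50 is equally far from both targets and also goes to the later window, whereas the tied Days 22 and 36 go to the earlier one.

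The bound also makes the window narrower than the visit interval, so some schedules step over it. Estimand 2 handles discontinuation by treatment policy and is meant to use what was observed off drug. For participants in the gap, an NPI-C score taken 6 or 7 days after the target is set aside and a modelled value takes its place at Day 43.

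The target of day 10 is a second mismatch in the same table. It feeds the closest-to-target rule for the follow-up summaries.

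**Working it through.** **Boundaries.** Inputs are the target days and windows in Table 1. The formula is (earlier target + later target)/2, with the tied day going to the earlier window.

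| Targets | Midpoint | Table 1 |
|---|---|---|
| 15 and 29 | (15+29)/2 = 22 | 22 |
| 29 and 43 | (29+43)/2 = 36 | 36 |
| 15 and 43 (vital signs, CMAI-C, ADAS-Cog-14) | (15+43)/2 = 29 | 29 |
| 43 and 57 | (43+57)/2 = 50 | 48 |

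The formula reproduces every figure except the last.

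**Gap.** The window from 37 to 48 has 48 − 37 + 1 = 12 days, against 14-day spacing. Stopping before Day 35 means a last dose on Days 1 to 34. With the early withdrawal (EW) visit on the next day, EW visits fall on Days 2 to 35, which is 34 possible days. I stepped forward by 14 days from each, up to Day 57.

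- Counted from the EW visit (Protocol 4.1):
  - EW Day 7 gives 21, 35, 49.
  - EW Day 8 gives 22, 36, 50.
  - EW Day 21 gives 35, 49.
  - EW Day 22 gives 36, 50.
  - EW Day 35 gives 49.
  - None of these falls in 37 to 48. That is 5 of 34 (15%): three lead to Day 49 and two to Day 50.
- Counted from the last dose (column heading in the Schedule of Activities): last-dose Days 7, 8, 21 and 22 miss. That is 4 of 34 (12%).
- With a window of 37 to 50 (14 days), 0 of 34 miss under either count.

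**Number of participants.** The planned drop-out is 15% of 86, or about 13. If all stopped before Day 35, with evenly spread timing and full attendance, the expected numbers are 13 × 5/34 = 1.9 or 13 × 4/34 = 1.5.

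**Visits that vary.** I assumed each follow-up visit shifts independently by up to 3 days either way (200,000 simulated schedules). The share with no visit in the window is:

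| Count from | 37 to 48 | 37 to 50 |
|---|---|---|
| Last dose | 16.8% | 7.2% |
| EW visit | 18.4% | 8.1% |

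For 13 participants these are 2.2 and 2.4 against 0.9 and 1.0, so the narrow bound itself accounts for about 1.3.

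**Visit 7 target.** If the double-blind phase ends on Day 43, follow-up day 1 is Day 44 and Day 57 is follow-up day 57 − 43 = 14, not 10. The target matters only when two assessments share the window. With target 10, a Day 14 visit is 4 days away. A second visit on follow-up days 7 to 13 is at most 3 days away and would be chosen instead. On day 6 the distances tie and the later visit is kept.

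**Possible common source.** Follow-up day 10 is study Day 53, and (43+53)/2 = 48. Both entries would fit a Day 53 visit, which neither document schedules.

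**The case against.** The strongest reply is that the SAP never writes down a midpoint rule. It states only which visit wins within a window. That stands: the midpoint is a pattern, and the SAP is free to set another bound. But it gives no reason for 48. The one other exception, between baseline and Day 15, separates predose from postdose and is not a comparable split.

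Day 50 is a tie, so only Day 49 is plainly misplaced. On that stricter count 3 of 34 days (9%) are affected, not 5. The objection stands as far as it goes, but the table gives its other tied days to the earlier window.

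One can doubt whether an off-drug score from Day 49 should stand for Day 43, since the Estimand 2 text speaks of data until Day 43. Yet Table 1 accepts Day 37 for Day 43 and Day 36 for Day 29, which are 6 and 7 days away.

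The count of about 2 is a ceiling under exact spacing. The 15% covers the whole six weeks, extra visits are only encouraged (Protocol 4.1, 7.1), and disallowed medication may be started after discontinuation. If that counts as a treatment switch, Estimand 2 drops those data anyway.

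On the Visit 7 target, a reader might infer that day 10 lies outside any permitted visit. It does not. With both Visit 6 and Visit 7 allowed 3 days either way, Visit 7 can fall on follow-up day 54 − 46 = 8 to 60 − 40 = 20. A reader might also infer that the rebound summary is distorted. The documents do not establish this: the endpoint is change to the first follow-up visit, so an early unscheduled assessment could qualify whatever the target.

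**Conclusion.** The concern holds as a small inconsistency in Table 1. The Day 43 EW bound departs from the table's own pattern and opens a gap for EW visits on Days 7, 8, 21, 22 or 35. In that gap Estimand 2 has no observed Day 43 score and imputes one: reference-based for seltorexant, missing at random for placebo, in both cases conditional on earlier scores.

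The likely effect is 0 to 2 participants. This assumes about 13 drop-outs, evenly spread timing and attendance at the optional visits. A reader might infer that the primary result is exposed. It is not: SAP 5.3.1 limits Estimand 1 to data up to the double-blind disposition day, so EW follow-up scores do not enter it. Nor do these participants drop out of Estimand 2; they enter with an imputed Day 43 value.

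The Visit 7 target of 10 does not agree with the stated 14 days, but it has no effect unless a second assessment falls in the open follow-up window. The shared origin in a Day 53 visit is conjecture. Correction is worthwhile because Estimand 2 differs from Estimand 1 through just these off-drug scores, and they will be few.

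**What to change.** In Table 1:

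- Set Day 43 EW to 37 to 50 for NPI-12/SDI/C-SSRS and for NPI-C, and to 30 to 50 for vital signs.
- Start Day 57 EW at Day 51 in the same three blocks.
- Set the FU (DB) Visit 7 target to 14 in all four blocks that carry it (those three and PWC-20).
- Reconcile the footnote's Day 50-57 with these windows and with the Day 57 end of follow-up in SAP 1.2 and Protocol 4.1. As it stands, the footnote lets Day 50 count as the end of follow-up.

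The cost is 3 × 2 + 4 = 10 table cells and one footnote, with no new visits or data. The change closes the gap for exact 14-day spacing. With visits varying by up to 3 days it cuts missed windows by rather more than half (from 17-18% to 7-8%) but does not remove them.
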